7.1.2 Other variables

Baseline data

Before the participants are randomized following baseline data will be collected (*the brackets state the type of data*):

Variable	Measure	Type/scale	Source
Diagnosis	ICD-10; established through clinical exam/CAT scan	Categorical	A
Gender	Male/Female	Categorical	A
Birthdate		Date	A
Symptom onset		Date/time	A/B
Admission		Date/time	A
Living arrangement	Living alone; living with partner; care facility; other	Categorical	B
Performance status (prior)	WHO performance status	Ordinal	B
Self-rated health	Two item questionnaire	Ordinal	B
Alcohol consumption (/week)	Within/above recommended level (7/14 units/week)	Categorical	B
Smoking	Daily; weekly; Rarely; Former; Never smoked For current smokers the amount and type of tobacco is also recorded	Categorical	B
Physical activity		Ordinal	B
Comorbidities	Charlson's Comorbidity Index: Aggregated scale based on weighted scores of presence or non-presence different diseases Individual diseases or groups will be coded as Y/N and the CCI will be calculated from these	Ordinal	A/B
Body weight	Measured (kg)	Continuous	C
Height	Measured (cm)	Continuous	C
Waist + hip circumference	Measured (cm)	Continuous	C
Stroke severity	Scandinavian Stroke Scale; Sub-scores: Consciousness, eye palsy, arm palsy, hand palsy, leg palsy, orientation, speech (dysphasia), facial palsy, gait	Ordinal	C
Vital signs	Early Warning Score; Sub-scores: Respiration rate, oxygen saturation, heart rate, temperature, systolic/diastolic blood pressure, consciousness	Ordinal	C
Cardiac rhythm	ECG: Normal; arterial fibrillation; other arrhythmia	Categorical	C
Blood glucose	S-glucose at admission; HbA1c	Continuous	C
Blood lipids	Total cholesterol, LDL, VLDL, HDL, triglycerides	Continuous	C

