1.4 Expected results

We expect to estimate the participation rate and variance of the blood pressure. These estimates will be used in planning a future randomized controlled trial.

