7.1 Variables

7.1.1 Outcome variables

Measures of feasibility

The primary outcome measure will be the rate of participation in the study; measured as:

- 1) the proportion of patients eligible for the study out of all patients with stroke admitted to the Department of Neurology,
- 2) the proportion of patients accepting to participate in the study, and
- 3) the degree of adherence to the intervention (proportion of attendance in follow-up sessions)

Aside from participation we will evaluate the participants' satisfaction with the overall intervention and single parts of the intervention.

Variable	Measure	Type/scale	Source
Admissions	Number of patients admitted in the study period	Continuous	
Eligibility	Number of patients who would be candidates for participation	Continuous	
Recruitment	Number of participants recruited	Continuous	
Adherence	Number of participants completing the treatment Degree of participation	Continuous	
Satisfaction	Five level Likert Scale	Ordinal	

Secondary outcome

Measure of effect

The secondary outcome measure will be arterial blood pressure measured 12 weeks after the start of the intervention. The arterial blood pressure will be measured as a continuous variable in mmHg. The participant should be sitting still and resting for ten minutes before the measurement. To avoid extreme values the measurement will be repeated three times with a few minutes apart and the median value will be used for the statistical analysis.

This outcome measure was chosen because hypertension is the most significant risk factor for stroke and TIA (5) and because previous studies have found that it might be possible to lower the blood pressure through lifestyle interventions (8).

Tertiary outcomes

Tertiary outcomes after 12 weeks will include:

Variable	Measure	Type/scale	Source
Changes in behavior			
Smoking	Daily; weekly; Rarely; Former; Never smoked	Categorical	B
Physical activity	Questionnaire	Ordinal	B
Adherence to medication	Questionnaire	Continuous	B
Anthropometric measures			
Body weight	Measured (kg)	Continuous	C
Height	Measured (cm)	Continuous	C
Waist + hip circumference	Measured (cm)	Continuous	C
Patient reported outcomes			
Fatigue	Questionnaire		B
Self-rated health	Two item questionnaire	Categorical	B

Secondary outcomes after one year will include:

Variable	Measure	Type/scale	Source
New stroke/TIA	Event + days till event	Categorical/time	A
Cardiac admission	Event + days till event	Categorical/time	A

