8.3 Statistical analysis

Hypothesis testing for the secondary outcome (systolic blood pressure) will be done as intention-to-treat (including all participants allocated) using a paired t-test comparing baseline systolic blood pressure with systolic blood pressure measured after 12 weeks. Results will be reported as mean difference of changes with 95 percent confidence intervals.

Tertiary outcome measures will be analyzed as intention-to-treat using unpaired student t-test for continuous variables and either chi-squared test or fisher's exact test for categorical variables. Treatment allocation will be blinded to the investigator.

Statistical analyses will be done in R 3.3.1/R Studio 0.99. A significance level of 5 percent will be considered statistically significant.

9 Validity and bias

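### Does the baseline systolic pressure used in 8.3 lack a measurement procedure matched to the 12-week value?

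*Combined protocol and SAP*

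**What the plan says.** The effect outcome is defined in 7.1.1: "The secondary outcome measure will be arterial blood pressure measured 12 weeks after the start of the intervention". The same paragraph says that pressure is recorded as a continuous value in mmHg and sets the conditions: "The participant should be sitting still and resting for ten minutes before the measurement", and "the measurement will be repeated three times with a few minutes apart and the median value will be used for the statistical analysis".

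The baseline list in 7.1.2 opens with "Before the participants are randomized following baseline data will be collected". Blood pressure appears there once, in the vital-signs row: "Early Warning Score; Sub-scores: Respiration rate, oxygen saturation, heart rate, temperature, systolic/diastolic blood pressure, consciousness". That row is typed as ordinal and has source C, which 7.2 defines as clinical or para-clinical examination. Section 7.2 also has all data collected by a study investigator.

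Section 8.3 tests systolic pressure "using a paired t-test comparing baseline systolic blood pressure with systolic blood pressure measured after 12 weeks" and adds: "Results will be reported as mean difference of changes with 95 percent confidence intervals". Section 1.3.4 describes a t-test of blood pressure between the groups. Section 1.4 gives the planning use: "We expect to estimate the participation rate and variance of the blood pressure".

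**The concern.** An analysis of change needs two comparable measurements. At 12 weeks the plan prescribes posture, rest, three readings and a median. At baseline, on a literal reading, it offers a component of a ward observation score. Weight, height and circumferences have their own continuous rows both at baseline and at 12 weeks, whereas the effect outcome has no such row at baseline. A data-capture form built strictly from 7.1.2 might have no field for three rested readings.

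If an unrested single reading were set against a rested median, the change score would carry extra error and its confidence interval would widen. A systematic difference between the two procedures would also appear as change within each arm. A matched pre-randomisation value cannot be obtained afterwards.

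**Working it through.** **What the text supports.** The plan gives no figure on this point, so the passages come first.

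- Only the opening sentence of the 7.1.1 paragraph is tied to 12 weeks. The sentences on units, rest, repetition and the median carry no time point.
- The median rule governs the value that enters the statistical analysis. The analysis of systolic pressure in 8.3 uses baseline and 12 weeks, so the rule reads naturally as covering both.
- Source C points to an examination and not to a figure taken from the medical record (source A).
- The 7.1.2 table gives no measurement procedure for any examined variable (weight and waist, for example). Its silence on blood pressure is the table's format and not evidence of a second procedure.
- No passage says that baseline pressure is measured differently.

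**Between-arm bias if baseline were unstandardised.** Let the recorded baseline be the true value plus a shift d plus error. Each change then contains −d. Baseline precedes allocation, so d has the same expectation in both arms, and the difference in mean change contains −d + d = 0. In 200,000 simulated trials with a common 5 mmHg shift, the between-arm t-test on change rejected 4.96% of the time, against a nominal 5%.

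**Precision if baseline were unstandardised.** Inputs:

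- SDs 18.3 and 21.5 mmHg (8.1), pooled: √((18.3² + 21.5²)/2) = 19.96.
- 20 per arm: 40 participants, equal split assumed.
- Correlation r between baseline and 12 weeks: 0.3, 0.5, 0.7 (assumed).
- Added independent baseline error SD e: 3.7, 5, 10 mmHg (assumed).

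SD of change = √(2(1 − r) × 19.96² + e²). Half-width of the 95% interval = t(0.975; 38) × SD of change × √(2/20).

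| r | e = 0 | e = 5 | e = 10 | Widening at e = 3.7 / 5 / 10 |
|---|---|---|---|---|
| 0.3 | 15.12 | 15.46 | 16.42 | 1.2% / 2.2% / 8.6% |
| 0.5 | 12.78 | 13.18 | 14.29 | 1.7% / 3.1% / 11.8% |
| 0.7 | 9.90 | 10.40 | 11.79 | 2.8% / 5.1% / 19.1% |

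Half-widths are in mmHg.

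**Which values of e are plausible?** For normal readings with SD σ, the median of three has variance 0.449σ². Using one reading instead adds (1 − 0.449)σ², an added SD of 0.742σ. With σ = 5, e = 3.7. For e = 5, σ must be 6.7, and for e = 10, σ must be 13.5. The documents give no σ. The upper end would probably need differences in rest or posture as well.

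**With baseline as a covariate instead of change.** The correlation falls to r × 19.96/√(19.96² + e²). The ratio of (1 − r²) after to before, for e = 5 and 10, is 1.006 and 1.020 at r = 0.3, 1.020 and 1.067 at r = 0.5, and 1.057 and 1.193 at r = 0.7. That is a rise in variance of 1–2%, 2–7% and 6–19%.

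**Planning the full trial.** Section 1.4 refers to the variance of blood pressure, not of change. The calculation in 8.1 compares two means and contains no correlation or change score: with 4.21 mmHg, SD 18.3 in both arms, two-sided 5% and 80% power, the normal formula gives 297 per group and the t-test version 298, the stated figure. An inflated SD of change does not enter that method, and the 12-week SD does not depend on how baseline was measured.

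**The case for a change.** The best case for acting is that it is cheap and the loss is permanent. The remedy would be a row on the case report form and a sentence or two. If the team already intends the 7.1.1 procedure at baseline, only wording is spent. If it does not, the matched reading is gone. The literal text of 7.1.2 does not rule out a form without the right fields, and 8.3 leans on the baseline value more heavily than a plain 12-week comparison would.

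Part of this stands. The extension to baseline is never stated, and it is sensible for the investigators to confirm it when they build the form. What does not stand is that the plan directs an unstandardised baseline. The harmful scenario requires investigators to examine the patient, know the rule for the analysed value, and then not apply it to one of the two values analysed. A within-arm paired test would indeed read a procedural shift as change, but it would do the same with any change common to both arms. That weakness belongs to the wording of the test in 8.3, and a matched cuff procedure would not cure it.

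**Conclusion.** The concern describes a true omission that calls for no change. The general wording of 7.1.1, the use of both time points in 8.3 and the examination source in 7.2 lead a sensible team to the same procedure at baseline. If they did not follow it, the between-arm contrast would remain unbiased under a common shift. The interval for the difference in change would be about 1–3% wider for an added error SD of 3.7 mmHg, and 2–19% wider for 5–10 mmHg, across r of 0.3 to 0.7. Neither the added error nor r comes from the documents, and the 19% is the extreme corner of both. The half-width is at least 9.9 mmHg even with no added error, well above the 4.21 mmHg effect cited in 8.1, so this point does not decide whether a 40-patient feasibility study can detect that effect. The participation and adherence outcomes, the 12-week comparison in 1.3.4 and the 12-week SD are unaffected.

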7.2 Data collection

All data will be collected by one of the study investigators using electronic case report forms (eCRF) on the RedCap platform. Only consent forms will be on paper.

The sources of data will be either:

- A) Electronic medical records. At this point it is not technically possible to transfer data from the electronic medical records and the data therefore to be entered manually using the eCRF,
- B) Structured interviews with the patients (and relatives if allowed) using standardized questions,
- C) Clinical or para-clinical examinations of the patient

7.3 Database construction and handling

Identifiable data (Names and CPR numbers) will be kept separate from any sensitive data. It will be kept in a key file on another data drive on another server than any other data.

Electronic data will be stored on a Region Hovedstaden server with automatic access logging and data back-up. Access to the data will be password protected using Region Hovedstaden user id (BAM ID).

All paper forms (*consent forms*) will be stored in a locked cabinet in the Department of Neurology at Nordsjællands Hospital.

7.4 Data control and editing

To avoid extreme values the eCRF will have set ranges of plausible values for numerical variables and it will not be possible to enter values outside the ranges.

Before data analysis the data will be checked for missing values. If values are missing we will attempt to reconstruct the information from medical records or by contacting the participant.

The data will be tested for abnormal values by the primary investigator:

Dates – The dates of symptom onset, admission, and discharge will be compared to ensure the differences are not unrealistically bigger than expected, and by testing if any dates are outside the study period.

Categorical variables – Will be checked for missing or illegal values with frequency distributions

Numerical variables – Will be checked for extreme/illegal values with summary statistics and by histograms/boxplots

7.5 Data processing for statistical analysis

The primary outcome measure is systolic blood pressure, which is rarely normally distributed. To make it normally distributed before analysis it should probably be transformed using the natural logarithm.

8 Statistical analysis

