1.3.4 Statistical analyses

Student t-test will be used as significance test for differences in blood pressure between the treatment groups.

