8.1 Sample size calculations

The study in the current form is a randomized feasibility study where the main objective is to test if the intervention and study design is feasible enough for a full size study randomized controlled trial. We will therefore only include 40 participants in this phase of the study.

A full size randomized controlled trial will no doubt require a larger sample size if we were to expect an effect to be found. In a meta-analysis of fairly similar interventional studies Lawrence et al. found that the weighted means of the systolic blood pressure were 132.5 (SD 18.3; n=682) mmHg in the intervention groups and 136.2 (SD 21.5; n=725) in the control groups, respectively, and with a mean difference of 4.21 mmHg (95%CI 2.18-6.24).

Using the estimates from Lawrence et al. we can estimate the sample size needed with the method for comparing two means as reported by Kirkwood & Stern ((12)p 420) with the following assumptions:

- An equal number of participants are allocated to the two groups
- The blood pressure values are approximately normally distributed
- An alpha of 5 percent (probability of Type I error) and a beta of 20 percent (probability of Type II error)

From this it is estimated that we will need a sample-size of 596 (298 in each group), not adjusting for losses to follow-up.

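### Do the primary label and the hedged log transformation in section 7.5 leave the blood pressure analysis undefined?

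*Combined protocol and SAP*

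**What the plan says.** Section 7.5 has two sentences: "The primary outcome measure is systolic blood pressure, which is rarely normally distributed", and then "To make it normally distributed before analysis it should probably be transformed using the natural logarithm". It gives no criterion for deciding.

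The outcome hierarchy is set in section 7.1.1. On feasibility it says "The primary outcome measure will be the rate of participation in the study"; on effect, "The secondary outcome measure will be arterial blood pressure measured 12 weeks after the start of the intervention", recorded in mmHg as the median of three readings. The summary in 1.3.2 names participation and adherence as the primary feasibility measures and systolic pressure as the primary measure of effect.

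The test appears in two places. Section 1.3.4 says "Student t-test will be used as significance test for differences in blood pressure between the treatment groups". Section 8.3 begins "Hypothesis testing for the secondary outcome (systolic blood pressure) will be done as intention-to-treat" and ends "Results will be reported as mean difference of changes with 95 percent confidence intervals". Neither mentions a logarithm, a ratio or a back-transformation, and 8.3 names no unit.

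Section 8.1 sizes a later full trial, not this one. It works in mmHg, "with a mean difference of 4.21 mmHg", and assumes approximate normality. Section 1.4 says the variance of blood pressure found here will feed that planning.

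**The concern.** Two things look wrong.

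- **Label.** One section calls systolic pressure primary and two call it secondary. In a confirmatory trial that would matter, because the primary outcome carries the alpha and the sample size.
- **Scale.** The hedge in 7.5 is not a decision. On logs, a difference of changes back-transforms to a ratio of geometric mean ratios, that is, a relative change. Untransformed, it is a difference in mmHg. If the choice waits until the data are seen, the more favourable version could be reported. Section 7.5 also calls the variable rarely normal, while 8.1 assumes approximate normality.

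At stake would be a data-driven choice of effect measure, and a variance estimate on a scale that the planning in 8.1 cannot use directly.

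**Working it through.** **1. The label.** Sections 7.1.1 and 8.3, which define and test the outcome, agree that blood pressure is secondary. Section 1.3.2 is compatible with them because it says primary for effect. Section 7.5 reads as that phrase without its qualifier. The sample of 40 is justified in 8.1 by the feasibility aim, and 8.3 applies one 5% level with no division between outcomes. Relabelling would alter no calculation.

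**2. The plan's own figure.** Section 8.1 gives 298 per group. With the 4.21 mmHg difference, SD 18.3 in both arms, two-sided 5% and 80% power:

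n = 2 × (1.960 + 0.8416)² × 18.3² / 4.21² = 2 × 7.849 × 334.89 / 17.724 = 296.6, so 297.

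The t-based version gives 297.6, so 298. The calculation was therefore done in mmHg. (Using both cited SDs gives about 353; that gap is a separate matter.)

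**3. How far from normal?** The SDs and means in 8.1 give coefficients of variation (CV) of 18.3/132.5 = 0.138 and 21.5/136.2 = 0.158. If pressure were exactly log-normal, its skewness, 3CV + CV³, would be 0.417 and 0.478. That is mild, so the approximate normality of 8.1 and the caution of 7.5 are not far apart in practice. These figures describe single readings. Section 8.3 analyses changes within patients, where much of the skewness cancels: if baseline and follow-up are exchangeable, the change is symmetric on either scale.

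**4. Do the scales measure different things?** Yes. 4.21/136.2 is a 3.1% reduction. Held as a fixed percentage, it is 120 × 4.21/136.2 = 3.7 mmHg at 120 mmHg and 160 × 4.21/136.2 = 4.9 mmHg at 160 mmHg (120 and 160 are assumed values).

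**5. Does the choice alter the test in this trial?** Hardly. The simulation assumed 20 patients per arm, the SDs and the 4.21 mmHg difference from 8.1, a correlation of 0.5 to 0.7 between baseline and follow-up, and normal or log-normal pressures. Between-group t-tests on untransformed changes and on log changes agreed at the 5% level in about 97 to 98% of runs. Power was about 9 to 13% on either scale.

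**6. Does it alter planning of the full trial?** Not in a stable direction. Assume log-normal pressures with means 136.2 and 136.2 − 4.21 = 131.99. The per-group n is 7.849 × (sum of variances)/(difference)², where the SD of the log is √ln(1 + CV²) and the geometric mean is mean/√(1 + CV²).

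| Assumed spread | n, log scale | n, mmHg | Log relative to mmHg |
|---|---|---|---|
| SDs 18.3 and 21.5 | 7.849 × (0.1380² + 0.1569²)/0.02861² ≈ 419 | 7.849 × (18.3² + 21.5²)/4.21² ≈ 353 | +19% |
| SD 19.96 in both arms | 7.849 × (0.1504² + 0.1458²)/0.03208² ≈ 335 | 353 | −5% |
| CV 15% in both arms | 354 | 358 | −1% |

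Here 19.96 = √((18.3² + 21.5²)/2), and the 15% is an assumption. The first row's increase comes from the unequal CVs together with the assumed log-normality, which the documents do not state. Nothing in the plan says the full trial would be sized on logs.

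**The case for a change.** The strongest case for acting is that the plan tests blood pressure at 5%, lists the effect on it as its second objective, and intends to reuse its variance, so the scale should be fixed in advance. The mmHg in 7.1.1 describes how pressure is measured. It does not say what is done to the values before analysis, and a median of three readings can still be logged. The histograms and boxplots in 7.4 are there to find errors, not to choose a transformation. A sentence naming the scale would cost almost nothing.

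Most of this stands as description. Section 7.5 does not decide, 8.3 names no unit, and the plan does not promise an SD in mmHg if logs are used. The consequence is what fails. The later and more specific section, 8.3, reports a mean difference and mentions no log; read with 7.1.1 and 8.1, its natural unit is mmHg. If an analyst took the log route instead, the t-test would remain a valid comparison of groups and the estimate would be reported as a ratio. Because readings are stored in mmHg, the SD for planning can be computed either way. A choice made after seeing the data is possible in principle, but it would seldom move the significance verdict.

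**Conclusion.** The concern describes the text correctly, but it does not call for a change. The label is a clerical slip that affects no decision. The open scale is a gap that a competent analyst fills from 7.1.1, 8.1 and 8.3, and both ways of filling it are sound.

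The effect is small: about 2 to 3% of simulated trials changed their 5% verdict with the scale, in a study that has little power for blood pressure on either one. This rests on the assumed 20 per arm, the assumed correlations and the spread cited in 8.1. For a confirmatory trial with blood pressure as its primary outcome, the scale would need to be fixed beforehand. For this feasibility trial of 40 patients, naming it would be tidier wording and nothing more.
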